10.3 Concomitant Medications

Concomitant medications will be coded according to therapeutic area using the WHO drug reference list. Concomitant medications will be presented in data listings and summarized by frequency counts according to anatomical and therapeutic area for all subjects dosed.

10.4 Extent of Exposure

Descriptive statistics will be presented to summarize the volume (mL) of IP/IMP administered. Dose administration for IP/IMP will be listed for each injection by subject. The peak dose of dobutamine and total dose of atropine will be summarized and listed for each subject.

10.5 Safety Analysis

The safety data will be summarized for all subjects dosed. Summary tables, including clinically significant changes wherever applicable, will be presented for the following safety endpoints:

- Adverse Events
- Clinical Laboratory Evaluations
- Electrocardiograms
- Vital Signs
- Special Situations

For vital signs and ECGs, the baseline for time points at rest will be the last measurement prior to the IP/IMP administration at rest; while the baseline for time points at stress will be the measurement which is collected after administration of the pharmacologic stress agent, dobutamine, and prior to LUMASON administration at stress (CE-DSE). All adverse events will be coded by MedDRA and summarized by system organ class and preferred term, by intensity and by causal relationship to the IP/IMP. Adverse event will be summarized separately for the NIMP(s). Only those events which occur from the start of IP/IMP administration through the follow-up period defined in the protocol will be tabulated in the Clinical Trial Report as “adverse events” see Section 9.1.1.

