6.5 Administration

Once reconstituted, LUMASON will be administered as a single 2 mL bolus injection during the rest examination, and then again as a single 2 mL bolus injection after peak stress is achieved with the administration of the stress agent, dobutamine (with or without the addition of atropine), and the UE-DSE stress examination is completed. Each LUMASON injection will be performed intravenously through a peripheral line using a 20 gauge catheter followed immediately with 5 mL of saline in order to flush the intravenous line of any remaining contrast agent. There will be at least a 30 minute period between the rest and the stress LUMASON injections.

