8.4.5.3 Vital Signs

Collect blood pressure and heart rate at the time points listed below. Obtain all the vital signs in a position that is consistent for all time points for each subject.

Rest echocardiography:	within 1 hour prior to the Rest LUMASON (CEUS) administration 30 minutes after the Rest LUMASON (CEUS) administration
Stress echocardiography:	immediately prior to the Stress LUMASON (CE-DSE) administration 30 minutes after the Stress LUMASON (CE-DSE) administration 1 hour after the Stress LUMASON (CE-DSE) administration* 24 hours after the Stress LUMASON (CE-DSE) administration*

**If stress echocardiography (CE-DSE) is not performed, obtain vitals at 1 and 24 hours after the rest LUMASON administration.*

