8.4.5.5 Electrocardiograms

A 12-Lead electrocardiogram (ECG) will be performed in all subjects at the following time points:

Rest echocardiography: within 1 hour prior to the Rest LUMASON (CEUS) administration
30 minutes after the Rest LUMASON (CEUS) administration

Stress echocardiography: immediately prior to the Stress LUMASON (CE-DSE) administration
30 minutes after the Stress LUMASON (CE-DSE) administration
1 hour after the Stress LUMASON (CE-DSE) administration*
24 hours after the Stress LUMASON (CE-DSE) administration*

**If stress echocardiography (CE-DSE) is not performed, obtain ECGs at 1 and 24 hours after the rest LUMASON (CEUS) administration.*

ECG examinations will be evaluated by a central ECG laboratory that will provide the ECG equipment to the site and will employ a cardiologist to perform the centralized ECG evaluation containing the following information:

- RR interval
- PR interval
- QRS interval
- QT and QTc interval (Bazett's and Fridericia's)
- Overall diagnostic assessment
- Comparison to Baseline

Attach a photocopy of the ECG reports to the appropriate page of the CRF. A dual snap electrode will be supplied to the site by the central ECG laboratory in order to allow the acquisition of both discrete (static) 12-lead ECGs and continuous ECG monitoring described in section 8.4.5.6.

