8.5.2 Pharmacologic Stress with Dobutamine

For stress, dobutamine will be administered intravenously by infusion pump at least 30 minutes after the rest LUMASON administration starting at a rate of 5 µg/kg/min. At 3 minute intervals, the infusion rate can be increased to 10, 20, 30, and 40 µg/kg/min to reach one of the following peak stress endpoints:

[figure not shown]
- Target heart rate: $0.85 \times (220 - \text{age})$;
- Development of new or worsening regional wall motion abnormalities;
- Peak dose;
- Significant arrhythmias;
- Severe hypertension (systolic blood pressure >200 mmHg or diastolic blood pressure >110 mmHg);
- Hemodynamically significant hypotension;
- Intolerable symptoms.

If a peak stress endpoint is reached, the test can be stopped before reaching the maximal dose of dobutamine. If no peak stress endpoint is reached after the maximum dose of dobutamine, 0.25 mg to 0.5 mg of atropine can be administered intravenously at peak infusion to increase heart rate. If peak stress is still not reached, atropine, in divided doses of 0.25 to 0.5 mg up to a total of 2.0 mg, should be used as needed to achieve target heart rate.

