8.5.3 Stress Echocardiography

Immediately after the administration of dobutamine, with or without the addition of atropine, a stress UE-DSE echocardiogram will be acquired at peak stress using harmonic imaging with the standard apical 4-, 2-, and 3-chamber views. Following the stress UE-DSE echocardiogram, a stress CE-DSE echocardiogram will be performed with administration of a single 2 mL bolus injection of LUMASON. A recording of 2D transthoracic harmonic echocardiography imaging will be performed from 30 seconds prior to injection of LUMASON and continue until all images are acquired. For both US-DSE and CE-DSE images, the apical 4-chamber view will be acquired first followed by the apical 2- and 3-chamber views.

Figure 1: Imaging Procedures

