9.8 Pulse Oximetry

If a worsening is observed during the continuous pulse oximetry monitoring, the Investigator will assess the worsening for clinical relevance (whether it meets the definition of an adverse event). Record all changes determined to meet the definition of an adverse event in the Adverse Event section of the CRF.

10 Statistical Methods

Summary statistics (mean, median, standard deviation, minimum, and maximum) will be provided for continuous variables, and the number and percentage of each category will be provided for categorical data. Unless otherwise specified, the statistical tests will be 2-sided at 0.05 level of significance.

Any changes in the original statistical methodology will be documented in the statistical analysis plan (SAP).

All statistical analyses will be performed using SAS® software.

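### The 24-hour vital-sign and ECG change is, as written, measured from a near-peak-stress baseline; Section 10.5 should assign that reading the resting baseline.

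*Combined protocol and SAP*

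**What the plan says.** Section 10.5 (Safety Analysis) defines two baselines for vital signs and ECGs. Rest time points use the last reading before the rest LUMASON dose. For the others, "the baseline for time points at stress will be the measurement which is collected after administration of the pharmacologic stress agent, dobutamine", taken before LUMASON is given at stress. There is no third rule for follow-up readings. The section promises summary tables, including clinically significant changes where applicable, but does not describe the change tables further.

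The only scheduled reading that fits the stress rule is the one "immediately prior to the Stress LUMASON (CE-DSE) administration" (Section 8.4.5.5, with the same time point in 8.4.5.3). Section 6.5 gives LUMASON at rest and "then again as a single 2 mL bolus injection after peak stress is achieved with the administration of the stress agent, dobutamine", once unenhanced stress imaging is complete. Section 8.5.3 says that "a stress UE-DSE echocardiogram will be acquired at peak stress". The stress baseline is therefore at or near peak stress.

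The reading "24 hours after the Stress LUMASON (CE-DSE) administration" is listed in Sections 8.4.5.3 and 8.4.5.5 under the stress echocardiography heading. Appendix C places the 24-hour column under Follow-Up. If contrast stress imaging is not performed, all three places time the 1-hour and 24-hour readings from the rest dose. Section 10.5 does not say which baseline those readings take.

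**The concern.** A baseline taken just before a dose isolates what happens after that dose only while other conditions stay roughly the same. At 30 minutes and 1 hour the choice is reasonable, because it keeps the onset of the dobutamine effect out of the LUMASON change. A day later the comparison answers a different question. The subject is no longer under stress, so the change is mostly the distance between peak stress and ordinary life. A heart rate still above the subject's own resting level is tabulated as a fall, and a flag for clinically significant change built on that difference could miss it.

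Safety data in dobutamine stress echocardiography with LUMASON are a stated secondary objective (Section 4). The 24-hour reading is the last scheduled vital-sign and ECG measurement, so its change table should be interpretable.

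**Working it through.** The plan gives no figure that depends on this baseline, so there is nothing of its own to reproduce. The check has two parts.

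**1. Which baseline applies at each time point**

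| Reading | Where scheduled | Baseline under 10.5 as written |
|---|---|---|
| 30 min after rest dose | Rest heading | Pre-rest-dose |
| 30 min and 1 h after stress dose | Stress heading | Pre-stress-dose (near peak) |
| 24 h after stress dose | Stress heading in 8.4.5.3 and 8.4.5.5; Follow-Up in Appendix C | Pre-stress-dose if the section headings are followed; no separate rule |
| 1 h and 24 h after rest dose, no contrast stress imaging | Footnotes in 8.4.5.3, 8.4.5.5 and Appendix C | Not stated; only a resting baseline fits |

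Subjects in the last row remain in the safety population, which Section 10.2 defines as everyone who receives LUMASON. One 24-hour change table can therefore contain both references.

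**2. Illustration for heart rate at 24 hours**

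Inputs: target heart rate = 0.85 × (220 − age), from Section 8.5.2. Resting rate is assumed to be 70 bpm, with a range of 60 to 80; the documents give no value. Tabulated change = 24-hour value − baseline.

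- Age 60: target = 0.85 × 160 = 136 bpm.
- Fully back at rest: 70 − 136 = −66 bpm. Against rest: 70 − 70 = 0.
- Still 20 bpm above rest: 90 − 136 = −46 bpm. Against rest: 90 − 70 = +20.

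Range over ages 45 to 75 (targets 148.75 to 123.25) and resting rates 60 to 80:

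- Back at rest: from 80 − 123.25 = −43.25 to 60 − 148.75 = −88.75 bpm.
- 20 bpm above rest: from 100 − 123.25 = −23.25 to 80 − 148.75 = −68.75 bpm.

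Not every subject reaches target. Section 8.5.2 says: "If a peak stress endpoint is reached, the test can be stopped before reaching the maximal dose of dobutamine". For a subject stopped on another endpoint at an assumed 110 bpm, with rest at 70, the two changes are 70 − 110 = −40 and 90 − 110 = −20 bpm. The effect is smaller, but the sign is still reversed in the second case.

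Mixing of baselines: take two subjects, both fully back at 70 bpm, one with contrast stress imaging (−66) and one without (0). Their mean tabulated change is (−66 + 0) / 2 = −33 bpm, although neither differs from rest.

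Blood pressure has no fixed direction. A subject stopped for severe hypertension at 201 mmHg systolic, with an assumed resting value of 130 and a 24-hour value of 170, shows 170 − 201 = −31 against stress and 170 − 130 = +40 against rest. A subject stopped for hypotension could show the opposite. The direction for QTc is likewise not fixed.

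**The case against.** The strongest counter-argument is that the last reading before a dose is the standard baseline for that dose. This stands for 30 minutes and 1 hour. A reader might infer that the stress baseline is wrong throughout, or that a change from rest is needed at every time point after the stress dose. The documents do not support that: a resting comparison at 30 minutes and 1 hour would carry residual dobutamine or atropine effect, and in an open-label study with no control arm (Section 6.3) it would not isolate LUMASON either.

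Second, the information is not lost. Section 10 states: "Summary statistics (mean, median, standard deviation, minimum, and maximum) will be provided for continuous variables". For subjects with both readings, the 24-hour mean minus the pre-rest-dose mean gives the mean change from rest, and Section 10.8 puts the data in listings or tables. This is true for means, but it gives neither the spread nor the individual extremes of the change, nor a correctly referenced flag.

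Third, other safeguards exist. The investigator reviews worsening from before to after dosing (Sections 9.4 and 9.7), adverse events are monitored to 72 hours unless cardiac intervention comes first, and the central ECG read includes a "Comparison to Baseline". These reduce the risk that a clinical problem goes unseen. However, the investigator review does not say which of the two doses it refers to, the ECG comparison leaves its baseline undefined, and none of them plans a within-subject summary of change from rest.

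Fourth, Appendix C might be read as assigning a resting baseline at 24 hours, so that the documents contradict each other by a calculable number of beats. That goes too far. Appendix C is a visit schedule, and its Follow-Up heading sets no baseline. No passage assigns the resting baseline to the 24-hour reading. The inconsistency is in how the reading is classified.

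Finally, Section 10.8 defers data-handling detail to the SAP. No fuller baseline rule appears in the text supplied, but one set elsewhere cannot be excluded.

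**Conclusion.** The point holds for the 24-hour reading and for subjects without contrast stress imaging. Following Section 10.5 together with the headings of 8.4.5.3 and 8.4.5.5 gives a 24-hour change that mainly reflects recovery from dobutamine and can show a persisting rise over rest as a fall. In the worked case the tabulated value is 66 bpm below the change from rest, which is simply the gap between the target rate of 136 and the assumed resting rate of 70. The size rests on that assumed resting rate and on the subject having reached target. These are single-subject illustrations, not estimates of a cohort mean.

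This is a cheap improvement of low priority. The tables are descriptive, and neither the sample size (Section 10.7) nor the success criteria (Section 10.6.4) depend on them.

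**What to change.** In Section 10.5 or the SAP:

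1. State that the baseline for the 24-hour vital signs and ECG is the last reading before the rest LUMASON dose, and apply this to any summary of clinically significant changes at 24 hours.
2. State that the same resting baseline applies to the 1-hour and 24-hour readings when contrast stress imaging is not performed.
3. Keep the pre-stress-dose baseline for 30 minutes and 1 hour after the stress dose. A change-from-rest column there is optional; if added, footnote that it includes residual dobutamine or atropine effect.
4. Classify the 24-hour reading in the same way in Sections 8.4.5.3 and 8.4.5.5 and in Appendix C.

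The cost is a few sentences and slightly more table work. No new measurement is needed, because every reading is already scheduled. The limitation is that, without a control arm, neither baseline separates a LUMASON effect from everything else that happened between the two readings.

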10.6 Efficacy Analysis

The echocardiographic images will be assessed by 3 off-site blinded readers independent of the investigational sites; accordingly, the efficacy analysis will be performed separately for each off-site reader. An additional, fourth, blinded reader will assess the coronary angiography images and provide a diagnosis of CAD.

10.6.1 Primary Efficacy Endpoint – Sensitivity and Specificity for Detection and Exclusion of CAD

10.6.1.1 Truth Standard Diagnosis

For subjects with coronary angiography as the truth standard, a subject will be diagnosed by the blinded off-site coronary angiography reader as Positive if percentage diameter stenosis of any of the vessels (RCA, LAD, LCx and LM) is $\geq 50\%$; otherwise, a subject will be considered as Negative.

For the remaining subjects who didn't have coronary angiography as the truth standard, a subject will be Positive if the subject had cardiac death, documented myocardial infarction, documented

revascularization or need for revascularization during follow up; otherwise, the subject will be considered as Negative.

10.6.1.2 Evaluation of CAD

The overall diagnostic echocardiographic conclusion will be classified by the off-site readers as Normal, Abnormal or Unevaluable for unenhanced (UEUS and UE-DSE) and LUMASON-enhanced (CEUS and CE-DSE) echocardiography respectively.

The diagnostic performance of echocardiography (UE-DSE and CE-DSE) will be derived based on the diagnosis from stress echocardiography and diagnosis from truth standard (see Table E).

Table E: Cross Tabulation of Diagnosis: Truth Standard vs. Stress Echocardiography

Truth Standard (TS)	Stress Echocardiography		
	Normal	Unevaluable*	Abnormal
Negative	TN	FP	FP
Positive	FN	FN	TP

TN = true negative; TP = true positive; FN = false negative; FP = false positive

*Unevaluable is defined as: inadequate visualization of segments comprising all coronary artery territories due to motion artifacts, lateral wall drop out, swirling or attenuation artifacts.

The null hypothesis is that there is no difference in sensitivity/specificity between CE-DSE and UE-DSE at peak stress; the alternative hypothesis is that CE-DSE is superior to UE-DSE in terms of higher sensitivity/specificity:

$$H_0: \text{Diag}_{\text{CE}} - \text{Diag}_{\text{UE}} = 0,$$

$$H_a: \text{Diag}_{\text{CE}} - \text{Diag}_{\text{UE}} > 0;$$

where Diag_{CE} and Diag_{UE} denote sensitivity/specificity for CE-DSE and UE-DSE at peak stress respectively.

The sensitivity and the specificity along with their 95% confidence intervals (CIs) will be calculated, and the difference in sensitivity/specificity will be tested using McNemar's Chi-square 2-sided test.

In addition, inter-reader agreement for the detection/exclusion of CAD for CE-DSE and UE-DSE will be evaluated by kappa statistic.

10.6.2 Co-Primary Efficacy Endpoint – Critical Shift of Subjects with Suboptimal Images to Adequate Images

The co-primary endpoint: The proportion of subjects with suboptimal images (≥ 2 adjacent segments with inadequate LV EBD in any of the 3 apical views) at UE-DSE converted to adequate images (reduction of suboptimal adjacent segments to obtain adequate images) at CE-DSE will be estimated along with the 95% CIs.

Additionally, the following supportive analyses will be performed:

- proportion of subjects with optimal images at UE-DSE to suboptimal (≥ 2 adjacent segments with inadequate LV EBD in any of the 3 apical views) at CE-DSE in terms of LV EBD visualization will be estimated along with the 95% CIs.
- The percentage of patients with at least one segment with inadequate border delineation will also be summarized for each of the views for both UE-DSE and CE-DSE.
- Inter-reader agreement among 3 off-site readers on the critical shift of subjects with suboptimal images at UE-DSE to adequate images at CE-DSE will be evaluated by kappa statistic.

10.6.3 Secondary Efficacy Endpoints

For the secondary efficacy endpoint of change in total LV EBD scores at peak stress from UE-DSE to CE-DSE, the total LV EBD score is calculated as the sum of the individual scores (0, 1, or 2) assigned to each of the 17 ventricle segments with a range from 0 to 34.

For each blinded reader assessment, paired t-test will be used to compare total LV EBD score between the CE-DSE and UE-DSE. Summary statistics will be provided for the total LV EBD score from UE-DSE and CE-DSE. The change in total LV EBD score from UE-DSE to CE-DSE will be summarized along with the 95% CIs and tested by paired t-test. The cross tabulated (for UE-DSE vs. CE-DSE) distribution of the individual scores (0, 1, or 2) assigned to each of the 17 ventricle segments will be presented.

Inter-reader agreement among 3 off-site readers on the EBD score for each segment from UE-DSE and CE-DSE will be evaluated by kappa statistic.

10.6.4 Success Criteria

The study will be considered a success if:

- for the primary efficacy endpoint of sensitivity/specificity, CE-DSE is superior to UE-DSE for at least 2 out of the 3 blinded readers and for the same 2 readers a lower limit of 2-sided 95% CI for sensitivity/specificity is $\geq 50\%$ (a rate considered greater than chance);
- for co-primary efficacy endpoint of proportion of subjects with critical shift of suboptimal images at UE-DSE to adequate images at CE-DSE, for at least 2 out of the 3 blinded readers lower limit of 2-sided 95% CI is above 35%.

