10.7 Sample Size

Software nQuery Advisor 7.0 is used for sample size determination in this study.

As suggested by FDA during the type C meeting on 13Aug2014, and as also reinforced and documented in the official meeting minutes issued by FDA on 24Sep2014, this study needs to demonstrate 1) a significant improvement in diagnostic performance endpoints, i.e., sensitivity/specificity from unenhanced stress imaging (UE-DSE) to contrast-enhanced stress

imaging (CE-DSE) in term of detection and exclusion of CAD, and 2) lower the CI of CE-DSE sensitivity and specificity greater than 50% (a rate greater than chance).

For significant improvement in diagnostic performance endpoints, the null hypothesis is that there is no difference in sensitivity/specificity between CE-DSE and UE-DSE at peak stress; the alternative hypothesis is that CE-DSE is superior to UE-DSE in terms of higher sensitivity/specificity:

$$H_0: \text{Diag}_{\text{CE}} - \text{Diag}_{\text{UE}} = 0,$$

$$H_a: \text{Diag}_{\text{CE}} - \text{Diag}_{\text{UE}} > 0;$$

where Diag_{CE} and Diag_{UE} denote sensitivity/specificity for CE-DSE and UE-DSE at peak stress respectively.

With 2-sided significance level (alpha) of 5%, and the probability of a Type II error (β) of 0.20, assuming expected difference between CE-DSE and UE-DSE is 25%,¹ and the proportion of discordant pairs is 40%, 45 subjects will be needed for sensitivity/specificity respectively.

For lower CI of CE-DSE sensitivity/specificity greater than 50%, assuming sensitivity/specificity of CE-DSE = 65%, about 45 CAD positive subjects are needed to have 95% confidence that the lower limit of sensitivity >50%, and 45 CAD negative subjects are needed to have 95% confidence that lower limit of specificity >50%.

Assuming approximately 30% of subjects enrolled will be CAD positive,¹³ in order to obtain 45 CAD positive subjects, 150 subjects in total need to be enrolled. With a total of 150 subjects enrolled, this will also provide more than enough CAD negative subjects according to the above calculations. The prevalence of positive subjects will be tracked based on on-site CAD diagnosis from the truth standard and if less than 30% of subjects are CAD positive, additional subjects will need to be enrolled to obtain sufficient CAD positive subjects.

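### The primary success rule does not say whether CE-DSE must beat UE-DSE on both sensitivity and specificity, and the 50% floor does not fully close the gap

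*Combined protocol and SAP*

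**What the plan says.** The primary criterion in section 10.6.4 has two parts. The first is superiority: "for the primary efficacy endpoint of sensitivity/specificity, CE-DSE is superior to UE-DSE for at least 2 out of the 3 blinded readers". The second is a floor: "for the same 2 readers a lower limit of 2-sided 95% CI for sensitivity/specificity is" at least 50%. Neither part says both, each or either.

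The hypotheses do not settle it. Section 10.6.1.2 defines one generic quantity and states that "the alternative hypothesis is that CE-DSE is superior to UE-DSE in terms of higher sensitivity/specificity". Section 10.7 repeats this. The test is given in the same form: "the difference in sensitivity/specificity will be tested using McNemar's Chi-square 2-sided test".

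Only the floor is worded with 'and', in section 10.7, where the study needs to show "lower the CI of CE-DSE sensitivity and specificity greater than 50" percent.

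Several places suggest that both measures matter. Section 4 and the first co-primary endpoint in section 5.2 name sensitivity and specificity together. Section 5.4 aims for 45 CAD-positive and 45 CAD-negative subjects. Section 10.7 sizes 45 subjects for each measure and refers to both detecting and excluding CAD.

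**The concern.** This is the decision rule for the primary endpoint of a study meant to support a supplemental application. A result in which one measure improves significantly and the other does not passes on one reading and fails on the other.

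The case that matters most is a change in calling threshold. If contrast leads readers to call more studies abnormal without discriminating better, sensitivity rises and specificity falls. A rule satisfied by one measure, with no limit on loss in the other, could count that as better diagnostic performance. The question is whether the 50% floor already prevents this.

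**Working it through.** **Step 1. Reproduce the plan's figures.** Section 10.7 states "With 2-sided significance level (alpha) of 5%, and the probability of a Type II error (β) of 0.20". Its other inputs for the McNemar test are a 25-point gain and 40% discordant pairs.

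- Let p10 be the proportion correct on CE-DSE only and p01 the proportion correct on UE-DSE only. p10 + p01 = 0.40 and p10 − p01 = 0.25, so p10 = 0.325 and p01 = 0.075.
- Full enumeration of the uncorrected McNemar test gives power 79.4% at n = 44 and 80.4% at n = 45. The stated 45 is reproduced.
- Floor: 0.65 − 1.96 × √(0.65 × 0.35 / 45) = 0.511, above 50%, as stated.
- 45 / 0.30 = 150 subjects, leaving 150 − 45 = 105 CAD-negative.
- A CE-DSE rate of 65% with a 25-point gain implies a UE-DSE rate of 40%.

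**Step 2. What the floor lets through when it applies to both measures.** The smallest counts whose Wald lower limit reaches 50% are 29/45 (64.4%) for sensitivity and 63/105 (60.0%) for specificity. Observed specificity may therefore fall to 60%, from any starting value.

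**Step 3. A single data set that divides the two readings.**

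| Measure | UE-DSE | CE-DSE | Discordant pairs (gain v loss) | McNemar χ² | Lower 95% limit, CE-DSE |
|---|---|---|---|---|---|
| Sensitivity | 18/45 | 30/45 | 15 v 3 | 12²/18 = 8.0 (p = 0.005) | 52.9% |
| Specificity | 89/105 | 69/105 | 2 v 22 | 20²/24 = 16.7 (p < 0.001) | 56.6% |

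Both floors are met, sensitivity is significantly better and specificity is significantly worse. Correct diagnoses fall from 18 + 89 = 107 to 30 + 69 = 99 of 150. The reader passes if one measure is enough and fails if both are required.

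**Step 4. How often a pure threshold shift meets the primary criterion.** The shift holds discrimination constant in an equal-variance binormal model (my assumption). With sensitivity 40% and specificity 85%, d′ = −0.253 + 1.036 = 0.783. Moving sensitivity to 65% gives specificity Φ(0.783 − 0.385) = 65.5%. Assumptions outside the documents are the starting specificity, 24% discordance among negatives, any starting sensitivity above 40%, and reader correlation from 0 to 0.9. The simulation used 45 positives, 105 negatives, the same 2 of 3 readers, and the Wald floor on both measures (20,000 trials per setting).

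| Shift | One measure enough | Both required |
|---|---|---|
| Sensitivity 40% to 65%, specificity 85% to 65.5% | about 49–50% | 0% |
| Sensitivity 50% to 75%, specificity 88% to about 69% | about 80–88% | 0% |

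In both rows specificity is significantly worse for more than 99% of readers.

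**Step 5. Joint success under the plan's own assumptions** (40% to 65% on both measures, 40% discordance).

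- Superiority on both, one reader: 0.804 × 0.991 = 79.7% with 45 and 105 subjects. It is 0.804² = 65% with only 45 and 45.
- Superiority on both, 2 of 3 readers, before the floor: about 82–89% over correlations 0 to 0.9.
- Adding the floor on both: about 48%.
- Superiority on one measure with the same floor on both: about 53–55%.
- The floor alone, one reader: P(X ≥ 29 | 45, 0.65) × P(X ≥ 63 | 105, 0.65) = 0.598 × 0.880 = 53%. The floor, mainly on 45 positives, accounts for most of the shortfall.

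**Step 6. Multiplicity.** If one measure is enough, the per-reader chance of a favourable significant result with no true difference is 1 − (1 − 0.025)² = 4.9%, against 2.5% for one test.

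**The case against.** **The plan means both.** The objectives, the endpoint definition, the two enrolment targets and the sizing of each measure all point that way, and an either/or design would not need 45 of each. This stands as evidence of intent. A reader might infer that the plan openly allows success on either measure; the documents do not support that, because the text is ambiguous. But naming and sizing two measures does not say how they combine into a verdict.

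**The floor already protects specificity.** In part it does. A reader might infer that a shift such as sensitivity 45% to 70% with specificity 70% to 45% would pass. That happens often (roughly 73–82% of trials) only if the floor is also read as either/or. With the floor on both, as section 10.7 words it, the figure is about 0%. The shifts in step 4 still pass.

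**Requiring both would wreck the power.** A reader might compare about 47–49% under 'both' with 96–99% under 'either'. The higher figure drops the floor on the second measure. With the same floor on both, the comparison is about 48% against 53–55%.

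**A threshold shift is not the only mechanism.** Table E counts unevaluable images as errors, so rescuing them can raise both measures. That is fair, and no document figure supports the assumed starting specificities. It does not close the gap in the rule.

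**The border-delineation co-primary must also be met.** True, but a shift in diagnostic threshold does not affect it, so it gives no protection here.

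**Conclusion.** The concern holds as an ambiguity in the primary decision rule. The floor on both measures stops large specificity losses but permits smaller significant ones. Under the step 4 assumptions, the primary criterion could be met in about half to nearly nine-tenths of trials in which specificity is truly worse, if one measure is enough, and in none if both are required. The size depends on a starting specificity of 85–88%, which the documents do not give. The textual gap and the example in step 3 do not depend on the simulation model. The wording should be settled before reader results are compared with the truth standard.

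**What to change.** - In 10.6.4, state that CE-DSE must be superior to UE-DSE for both sensitivity and specificity, and that the lower 95% limit must be at least 50% for both, in the same two readers.
- In 10.6.1.2 and 10.7, replace the slash with 'sensitivity and specificity', and write the hypotheses as two that must both be rejected.
- In 10.7, state the joint probability of success with its assumptions. With 45 positives and 105 negatives it is about 82–89% before the floor and about 48% with the floor on both.
- If one measure is truly meant to suffice, pre-specify a no-loss margin on the other and a multiplicity rule.

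The cost is a wording amendment and a less favourable stated chance of success. The 'both' requirement itself takes about 6 points. The larger shortfall comes from the 50% floor with 45 positives at a true rate of 65%, and is present on either reading once the floor covers both measures.
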